RESEARCH PROTOCOL

STUDY TITLE

COMPETENCIES REQUIRED BY ANESTHESIOLOGISTS MANAGING CRITICALLY ILL MEDICAL AND SURGICAL PATIENTS IN AN INTENSIVE CARE UNIT: EXPERT CONSENSUS USING A DELPHI METHOD

INVESTIGATORS

[name] [name] (Principal Investigator)

[name]

[name]

[name] [name]

[name]

[name]

DOCUMENT DATED 09 August 2021

BACKGROUND

Critical Care Medicine (CCM) has emerged as an independent specialty over the last few decades. Anesthesiologists being perioperative physicians are an integral part of this progress, with many of them opting for CCM as a full-time career. [1] The coronavirus disease 2019 (COVID-19) pandemic has brought unprecedented challenges in the health care system. Anesthesiologists working in the operating room (OR) and those working in the Intensive Care Unit (ICU) have been the frontline workers along with other Critical Care professionals in the management of critically ill patients with COVID-19.

Though a few countries have recognized CCM as a separate specialty of medicine, in most countries, it is considered as a sub-specialty of broad specialties like Anesthesiology, Pulmonary Medicine or Internal Medicine. Some professional bodies have developed formal curriculum for training in CCM. [2, 3] The Competency-Based Training programme in Intensive Care Medicine (CoBaTrICE) from the European Society of Intensive Care Medicine (ESICM) is a widely accepted formal structured training curriculum in CCM. [3] Most curricula are designed only for high-income, well-resourced training and practice environments and do not account for additional skills and competencies that may be required to practice in resource variable settings, something the COVID-19 pandemic has demonstrated needs to be universal.

The transition of Anesthesiologists working in OR, or managing critically ill surgical/polytrauma patients, into working in ICU has largely been smooth. Nevertheless, deficiencies have been noted by experts in the Anesthesiology training in certain competencies required for the management of critically ill medical and surgical patients in the ICU. [4, 5] This is often compounded by considerable variation in the training curriculum of the Anesthesiologists based on the geographical region and type of institution.

There is a need to identify these competencies, so that Anesthesiologists who wish to practice full time or part time Critical Care, can acquire these competencies to improve

their ability to manage critically ill patients in ICU, in different WHO defined healthcare facilities levels. [6] This may also help provide guidance to educators worldwide regarding the competencies to be included in Anesthesiology training that may help Anesthesiologists work better with critically ill patients in ICU. These competencies have never been formally identified or published. We plan to review the existing competencies for CCM in the Anesthesiology curriculum across the globe through a preliminary survey. Thereafter, we plan to identify the additional competencies required through consensus among Experts, using a Delphi method. These additional competencies, classified as *mandatory*, *desirable*, and *optional* may serve as a guide for Anesthesiologists to practice Critical Care in ICU in different levels of health care facilities worldwide.

OBJECTIVES

1. To review / identify the existing competencies for CCM in the Anesthesiology curriculum across the globe.
2. To generate expert consensus on the additional competencies (mandatory desirable and optional) required for Anesthesiologists to practice Critical Care in ICU.
3. Provide guidance to educators worldwide regarding the competencies to be included in the Anesthesiology curriculum that may help Anesthesiologists work better with critically ill patients in ICU.

METHODOLOGY

Steering Committee

A Steering Committee comprising of Anesthesiologists with experience in CCM will be formed under the auspices of the Intensive and Critical Care Medicine Committee (ICCCM) of the World Federation of Societies of Anaesthesiologists (WFSA).

Selection of Experts

The Steering Committee will select global experts to participate in a Delphi process.

The selection criteria will include 1. Anesthesiologist (a medical graduate who has completed a nationally recognized Anesthesiology training programme) 2. Involved in the management of critically ill patients in ICU 3. More than ten years of experience in teaching and training in Critical Care. We aim for a total sample size of 30 experts for the Delphi rounds. Invitations to various global experts will be sent by email along with the study details and objectives of the Delphi process.

Preliminary survey

The Steering Committee will develop a preliminary survey to assess the knowledge and skills acquired by Anesthesiologists across the globe following Anesthesiology training, that is required to achieve the various Critical Care competencies. A literature review on the existing Critical Care competencies from various professional bodies will be conducted to develop a list of Critical Care competencies, using CoBaTrICE as a base.

Anesthesiologists who have completed their training within the last three years will be surveyed. The preliminary survey will be sent to approximately 500 Anesthesiologists across the globe by the Experts. Their competencies in CCM will be assessed under six domains in the survey. (*Disease diagnosis and management, Procedures, Monitoring and therapeutic interventions, Resuscitation, Communication and End-of-life care, Patient safety and Crisis Resource Management*) using a 5-point Likert scale (*never seen, have observed, can manage under supervision, can manage with minimal assistance, and can manage independently*). The first section of this survey will include the participant demographics, country of origin and training, year of completing training, and a few

training characteristics. The results of the survey will be used to draft competencies for inclusion in Round one of the Delphi.

The Delphi process

The Delphi process is a well-established methodology to generate consensus on a particular topic using the “collective intelligence” of panel members. [7-9] The steering committee members will perform a literature search on the available evidence, draft the initial statements and conduct iterative Delphi rounds to generate consensus among the experts. The Steering Committee members will not participate in the Delphi surveys themselves.

Steps of the Delphi process

Step 1: Establishing a preliminary list of competencies

A literature review on the existing Critical Care competencies from various professional bodies will be conducted to develop a list of Critical Care competencies, using CoBaTrICE as a base and categorized under the six core domains (*disease diagnosis and management, procedures, monitoring and therapeutic interventions, resuscitation, communication and end-of-life care, patient safety and crisis resource management*). The results of the preliminary survey will be used to draft statements for Round one of Delphi.

Step 2: Preparation of the Delphi Round one survey

The list of the competencies will be sent to the Experts as a Delphi questionnaire. The anonymity of the experts will be maintained during the Delphi rounds. The participant will be asked to score each of the competencies listed on a 5-point Likert scale (*non-essential, optional, optional but desirable, desirable, and mandatory*). The participating

expert will be invited to provide feedback regarding omission, addition, or modification of the items on the questionnaire. The response and feedback of experts will be collated during the analysis of results and shared in the following survey as controlled feedback.

Step 3: Subsequent Delphi Rounds

The steering committee will review the results of round one. The competencies listed will be modified, deleted, or added if found ambiguous based on the feedback and comments of the results. Competencies deemed “*non-essential*” by more than 50% of the respondents will be eliminated. The remaining competencies will be continued in the subsequent rounds until consensus is achieved (>80% of respondents). Lower-rated items identified for removal may be retained in the second round if they are considered “*mandatory*” by more than 20% respondents. The summary results of Round two will be presented to Experts, and the survey process will be repeated with the modified questionnaire. The Delphi rounds will be continued till desired consensus and stability is achieved for competencies.

Step 4: Final Consensus on Competencies to be included

The summary results of the last stable round will be used to issue the consensus on the additional competencies to be included. These competencies will also be classified as those *mandatory*, *desirable*, and *optional*, which may serve as a guide to decide which competencies are required for working in different levels of health care facilities worldwide. The results of the final survey, consensus competencies, and the manuscript will be circulated among the experts for approval before submission for publication.

Statistical analysis

A descriptive analysis of the preliminary survey will be performed. For the Delphi process, stability will be checked by non-parametric chi-square (χ^2) tests from round two onwards. A p-value <0.05 is considered as a significant variation or

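### Objective 1 asks what anesthesiology curricula contain, but the survey assigned to it rates what recent graduates can do, up to three years after training

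*Protocol*

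**What the plan says.** Objective 1 in the protocol is "To review / identify the existing competencies for CCM in the Anesthesiology curriculum across the globe". The last paragraph of the Background names the method: "We plan to review the existing competencies for CCM in the Anesthesiology curriculum across the globe through a preliminary survey". The same paragraph says that the additional competencies will be identified after that, by Delphi consensus.

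The Preliminary survey section gives the survey a different subject. It is to "assess the knowledge and skills acquired by Anesthesiologists across the globe following Anesthesiology training". On who answers, it says: "Anesthesiologists who have completed their training within the last three years will be surveyed". Respondents are assessed in six domains on a five-point scale: "never seen, have observed, can manage under supervision, can manage with minimal assistance, and can manage independently". The opening section of the questionnaire collects demographics, countries of origin and training, year of completion, and some training characteristics that are not listed. About 500 anesthesiologists are to receive it, and the Statistical analysis section plans a descriptive summary.

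Two other sources are described. One is a literature review: "A literature review on the existing Critical Care competencies from various professional bodies will be conducted to develop a list of Critical Care competencies", starting from CoBaTrICE. The other is a general literature search by the Steering Committee for drafting the Delphi statements (The Delphi process).

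**The concern.** Curriculum content belongs to a programme; ability belongs to a person. The Background itself treats curricula as differing between programmes when it refers to "considerable variation in the training curriculum of the Anesthesiologists based on the geographical region and type of institution". The two can part in either direction. A required topic may be rated as never seen because the trainee's hospital had no such cases. A topic outside the curriculum may be rated as fully mastered because it was learned in practice afterwards.

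Two things are at stake. Objective 1 is a stated objective in its own right, and it would be reported from data that do not measure it. Objectives 2 and 3 also lean on it: calling competencies additional presupposes a baseline of existing ones, and advice to educators on what to put in a curriculum depends on telling what is not taught from what is taught but not mastered.

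**Working it through.** No arithmetic applies. The check is whether the method named for objective 1 measures its target, and whether another described source does.

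1. **Target.** Objective 1 and the Background sentence both concern competencies existing in the anesthesiology curriculum worldwide.
2. **Method named for it.** The Background assigns this to the preliminary survey and to nothing else.
3. **What is rated.** The stated aim is acquired knowledge and skills. Of the five response levels, the first two describe exposure and the other three describe degrees of ability. None says that a competency was taught, required or part of the programme. The respondent rates himself or herself; no external assessor is mentioned.
4. **When it is rated.** Respondents are between zero and three years past completion. The ability levels are in the present tense, and no described wording ties the answer to the end of training. The aim's phrase about skills acquired following training can mean as a result of training or after it. On the first reading it is still individual attainment. On the second it includes later practice.
5. **What could separate training from later practice.** Year of completion allows respondents to be ordered by time since training. No named field records ICU or fellowship work since then. The unlisted training characteristics might include it, but the text does not say so.
6. **Other sources.** The literature review is described as covering critical care competencies, and the Background presents CoBaTrICE, its starting point, as a critical care training curriculum. The Delphi literature search is described only as covering available evidence. Neither is stated to review anesthesiology curricula, although neither is stated to exclude them.
7. **Route to the Delphi list.** Survey results help to draft round one items. Step 1 also builds the list from the literature, and in Step 2 the experts may propose omitting, adding or modifying items. The survey is therefore one input among several.

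Result: the target (step 1) and the measurement (steps 3 and 4) differ, and no source in step 6 is stated to supply what is missing. Step 7 limits how far this reaches the final list.

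**The case against.** The strongest reply is that this is largely a matter of terms. The protocol uses training and curriculum loosely: the Background speaks of competencies to include in training where objective 3 speaks of the curriculum. If objective 1 means what training delivers, asking recent graduates is a sensible approach, and the three-year limit already restricts later practice. This stands in part. The survey is a reasonable measure of training outcome, and the fault lies mainly in how objective 1 is worded. It does not remove the mismatch, because the objective as written would still be answered with a different quantity.

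A second reply is that the questionnaire has yet to be developed and a protocol need not list every field. That is fair for later ICU or fellowship work: whether it will be recorded is unknown, not ruled out. The response scale, the respondents and the objective are already fixed in the protocol, however, and a descriptive analysis cannot recover what was not asked.

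Three stronger readings are tempting and should not be drawn:

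- *That later practice has distorted the ratings, notably through COVID-19.* The Background says that anesthesiologists "have been the frontline workers along with other Critical Care professionals in the management of critically ill patients with COVID-19", but not how many recent graduates did this work, or whether before or after completing training.
- *That training and later practice can never be separated.* Year of completion and the unlisted characteristics leave that open.
- *That the Delphi list is invalid.* No passage derives the additional competencies by subtracting survey results from a list, and the list has other sources.

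**Conclusion.** The point holds as a mismatch between objective 1 and its instrument. Carried out as described, the survey would give the self-reported exposure and ability of recent graduates, possibly including skills gained after training. It would not show what curricula contain. Neither the size nor the direction of any resulting distortion can be fixed from the protocol, and the effect on the final Delphi list is probably small. The correction is worth making because it is cheap and can be made while the survey is still to be developed; the study as a whole is not threatened.

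The conclusion rests on the protocol's description of the survey, since the questionnaire is not shown. It assumes that the unlisted training characteristics do not record curriculum content competency by competency, and that the two literature sources are no wider than described. If either assumption is wrong, saying so in the protocol would settle that part.

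**What to change.** In the Preliminary survey section, word the ability items as referring to the time *at completion of your anesthesiology training*, and name ICU or fellowship work since training as one of the recorded characteristics. This reduces contamination by later practice and lets any remainder be examined.

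In the Objectives and the last paragraph of the Background, restate objective 1 and its matching sentence as identifying the self-reported critical care competencies of recent anesthesiology graduates. This limits the conclusion to what the survey can support.

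The cost is one extra field and some recall error among those furthest from completion; restating the objective changes wording only. The rewording is needed even if the items are anchored, because ability at the end of training is still not curriculum content.
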